What remain to be defined are the mechanisms that link developmental risk factors to the onset of symptomatology and to define developmental trajectories that reveal the expected effects on emotional and cognitive function, as well as potential protective factors. Not all children with prenatal adversity develop behavioural or cognitive disorders. We suggest that post-natal factors especially the quality of caregiver-child interactions are candidate mechanisms for the variation in psychopathological outcomes associated with prenatal factors. There is now a clear need to define developmental pathways by pre- and post-natal experience shapes vulnerability for psychopathology. Moreover, more vulnerable children, including those born at low birth weight, appear to be at increased sensitivity to the quality of the post-natal environment [16,17]. Thus, despite the link between fetal adversity and later psychopathology, there is good evidence for both continuities and discontinuities of psychopathology in the preschool age [18].

Evidence for this process comes from one of the few studies to examine the interaction between pre- and post-natal influences on neurodevelopment. One postulated mechanism includes decreased hippocampal volume [19] found in anxiety disorders and depression and one of the primary targets for both antidepressant and anti-anxiety medications. Interestingly, the effect of fetal growth on hippocampal volume is mediated by the perceived quality of maternal care [20]. In support of our proposed interaction between fetal growth and the quality of postnatal maternal care, we [20] reported evidence for an effect of birth weight on hippocampal volume in adult human subjects, that was moderated by the quality of perceived maternal (but not paternal) care. Thus, among individuals who reported a high quality of maternal care, there was no relation between birth weight and hippocampal volume. These findings are consistent with reports showing that the quality of the attachment relationship moderates

both the association between prenatal stress and fear reactivity and cognitive abilities [21]. Finally, this hypothesis is also consistent with the results of studies showing that interventions that target parenting have important outcomes for child development [17, 22].

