We will examine the role of mother-child attachment in the development of early psychopathology in children with and without prenatal adversity, defined by birth weight (corrected for gestational age). We will also focus on early manifestations of psychopathology in order to study possible factors that might modify the risk of psychopathology before these pathologies become entrenched, and associated with disability later on. Such studies are consistent with the increased capacity for neuroplasticity over early childhood. This is a major advantage of the prospective, longitudinal approach of the MAVAN study.

An additional feature of the MAVAN studies is that of understanding the factors that influence the quality of mother – child interactions. Thus, we examine the quality of the maternal environment using measures that are known as the best predictors of individual differences in maternal care and infant attachment. The best environmental measures are those of ‘marital’ support and stress. Since both factors appear to operate through maternal mental health, we also include measures of maternal well-being. While we focus on those measures that are specific to the 72-month protocol, measures of mother – child interaction, maternal environment and maternal well being have been included in MAVAN since the prepartum period.

Hypothesis 1: The relation between birth weight and measures of childhood mental health will be moderated by the quality of post-natal maternal care. We will focus on two outcomes measures, the Connors questionnaire and the DOMINIC/QUE questionnaire.

Hypothesis 2: The quality of postnatal mother – infant interaction will be influenced by the quality of the maternal environment and maternal mental well being.

Measures

We focus our description on measures that are new to the MAVAN study. This list of measures is complete, and we note where measures have been previously approved. Also, in accordance with the comments on the previous submission, we emphasize new measures.

Seventy-two month interview: Home visit (150 minutes)

Mothers

Interview: Questionnaire on Maternal Well-Being (30 minutes)

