Hypothesis 1: The relation between birth weight and measures of childhood mental health will be moderated by the quality of post-natal maternal care. We will focus on two outcomes measures, the Connors questionnaire and the DOMINIC-R questionnaire. We predict a significant interaction between birth weight corrected for gestational age x child attachment (secure versus insecure). Birth weight will be examined as a categorical variable using the following percentile groupings for birth weight for gestational age (0-20%, 21-40% and 41-70%). These percentiles are calculated using contemporary Canadian norms (Kramer, 2001). We have previously used these groupings to show significant effects of birth weight on tests of attention and impulse control. The results will be analyzed using a two way ANOVA (birth weight class) x attachment category, with a predicted interaction effect (post-hoc analyses) such that birth weight effects are apparent only amongst children showing insecure attachment. Subsequent ANCOVA's could be used to test the effects of possible moderators, including measures of sleep quality, which can affect mood as well as cognitive performance.

The same analysis will be applied to the results of the Connors Rating Scale, which is included as the current standard rating scale measure for symptoms associated with the Attentional Deficit Hyperactivity Disorder. The use of this measure also allows us to correlate a standard parent/teacher rating scale to the self-report measures of the child. Likewise, we predict a similar birth weight x child attachment interaction effect on the BRIEF (Behavior Rating Inventory of Executive Function) measure of executive function. A strength in this approach is that of the overlapping measures. While this implies greater number of statistical tests, this is the opportunity for the establishment of converging evidence should the predict interaction emerge in each of these analyses.

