The inclusion of the CASI permits a direct measure of potential cognitive mechanisms for individual differences in the risk for psychopathology. The questionnaire measures the inclination for positive/negative self-attribution, which is considered linked to the risk for affective illness (Seligman et al., 1984). We will use the positive – negative subscale scores in a multivariate analysis. If indeed cognitive attributional style is a mediator for the vulnerability reflected in the DOMINIC-R scales, then the inclusion of this measure, especially the negative scale, should significantly reduce the predicted interaction effect between birth weight and child attachment.

Hypothesis 2: The quality of postnatal mother – infant interaction will be associated with differences in the quality of the maternal environment and maternal mental well-being. We will essentially use an analysis similar to that for case – control studies, splitting data according to child attachment category (secure vs insecure). We will use independent t-tests to compare the data for mothers of secure versus insecurely attached children on the McMaster Model of Family Functioning (MMFF) with separate analyses of the six subscales of the MMFF (Problem solving, communication, roles, affective responsiveness, affective involvement, behaviour control) as well as on the General Functioning scale that measures the overall level of the family’s functioning. We predict significant differences across all scales. Subsequent analyses will explore the possibility that one subscale may be a better predictor of child attachment.

References

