**Maternal Adversity, Vulnerability and Neurodevelopment (MAVAN)
Project**

Investigators:

Principle Investigator: [name]; Co-Investigators: [name], [name], [name], [name], [name], [name], [name], [name], [name], [name], [name], [name], [name], [name], [name], [name].

Project funded August 1, 2004 through a CIHR Strategic Grant (750,000 per year for 5 years)

Research Project

Submitted for Approval by Douglas Hospital REB

February 25th, 2004

I. Introduction.

Objectives: The probability of chronic illness is strongly influenced by environmental conditions prevailing during development (Hertzman 1999). The frequency of heart disease, diabetes, and mental illness is substantially greater amongst those born and raised in poverty, regardless of social class in adulthood. Adversity associated with poverty produces incomplete, dysfunctional families often rife with domestic violence, malnutrition, drug use, child abuse and neglect. Reproduction within this context is associated with maternal stress, increased risks for infection and thus pre-term labour, perinatal deaths, birth insults, poor nutrition for mother and offspring, and serious compromises in the quality of parent-child interactions. These conditions define high-risk families. For the child, these conditions bear the potential to influence the development of physiological systems that regulate metabolism and cardiovascular function, as well as neural processes underlying emotion and cognition. These effects form the basis for vulnerability for illness.

Perhaps the most dramatic illustration of the relation between adversity in early life and the risk for later illness emerges from studies on birth weight, early growth and health in adulthood. Individuals that were small for gestational age, suggesting some degree of intrauterine growth restriction, are at significantly greater risk for type II diabetes, visceral obesity and hypertension (collectively referred to as the metabolic syndrome). The major predictors of fetal growth restriction and pre-term labour, are maternal stress, infections, malnutrition, and tobacco/alcohol consumption. These risk factors are far more prevalent in low socio-economic status (SES) families and, predictably, low SES is a major risk factor for both intrauterine growth retardation (IUGR) and pre-term labour.

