It is increasingly clear that growth restriction also predicts an increased risk for mood disorders (Thompson et al. 1997, and see Kelly et al. 2001). Additionally, the risk factors (i.e., maternal stress, tobacco/alcohol use, nutritional deprivation) for IUGR are also the major predictors for Attentional Deficit Disorder (ADD) and, predictably, ADD is far more prevalent in low SES environments (Biederman et al., 1990, 1995; Barkley 2000). Follow up studies of growth retarded infants reveal evidence for problems associated with attention and impulse control, functions that are heavily dependent on the hippocampus and prefrontal cortex. These same brain regions are also among the major sites implicated in both depression and anxiety disorders. Interestingly, growth restriction is also associated with increased behavioural inhibition, shyness and timidity in childhood, all of which appear to be predictors of mood disorders in later life. Studies with primate and rodent models show that the development of the hippocampus is impaired by fetal glucocorticoid exposure or by prenatal stress, and glucocorticoids are a mechanism for fetal growth restriction.

Glucocorticoids are a major class of stress hormones and the release of these hormones is activated by stress, as well as by protein deprivation, tobacco and alcohol. Thus, we propose *that impairments in the development of the hippocampus and prefrontal cortex serve as the mechanism for the relation between fetal growth restriction and impaired cognitive and emotional development.*

These studies suggest that endocrine conditions that promote fetal growth restriction can also compromise neural development. However, follow-up studies with even very low-birth weight babies reveal an impressive level of variability in cognitive outcomes. Evidence from clinical intervention studies with high-risk infants and developmental neurobiology suggests that neurocognitive development is influenced by the quality of the postnatal environment. Of particular relevance are the results of studies with primate and rodent models indicating that nurturing forms of maternal care can enhance neuronal survival and synaptic growth in regions such as the hippocampus (see below). Thus we propose *that the developmental outcomes associated with fetal adversity, reflected in growth retardation, are determined by the quality of the postnatal environment.*

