are consistently associated with cognitive impairments; the existing data suggest that cognitive outcomes are more seriously compromised by growth restriction than by prematurity (Lagercrantz 1997). Studies using more global measures of cognitive development, such as IQ tests, reported significant impairments among IUGR children (e.g., Breslau et al. 1996; Fattal-Valevski et al. 1999; Leitner et al. 2000;). van der Reijden-Lakeman et al. (1997) found that at 2 years of age, IUGR children were impaired on tests of divided, focused and sustained attention. On such tests, the IUGR population was less accurate and more impulsive than controls. These findings suggest that low-birth weight children might be at greater risk for the development of Attentional Deficit Disorder (ADD). Indeed, the risk factors for IUGR, including maternal stress, maternal psychopathology, protein malnutrition, tobacco/alcohol consumption are identical to those for ADD. Likewise, maternal stress during gestation is a predictor of both fetal growth restriction and negative temperament (irritability, negative emotionality) and anxiety in children (O'Connor et al. 2000; Glover et al. 2002). Behavioural disorders, characterized by poor impulsive control, shyness, timidity and negative temperament (greater frequency of negative emotional states) are positively related to the degree of growth restriction (e.g., Szatmari et al. 1990; Pharoah et al. 1994; Sykes et al. 1997).

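### Hypothesis 1's birth weight x attachment ANOVA has no term for SES or parental psychopathology, so its birth weight effects may partly reflect shared family risk; the interaction test is little affected

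*Protocol*

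**What the plan says.** **The model.** The Protocol (Analyses, Hypothesis 1) states: "The results will be analyzed using a two way ANOVA (birth weight class) x attachment category". It predicts birth weight effects only in insecurely attached children, and applies the same analysis to the Conners scale. The opening of the Analyses section adds stratification by gender. The DOMINIC-R text under Measures also predicts birth weight effects directly on several subscales.

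**Possible extra terms.** The same section adds: "Subsequent ANCOVA's could be used to test the effects of possible moderators, including measures of sleep quality". The NEPSY is called a potential covariate, standing for child IQ. The attributional style interview is treated as a mediator. The Family History Screen is collected under Measures but is not used in Analyses. The Combined protocol and SAP (IV. Statistical analysis) plans regression and ANOVA for its hypotheses, with structural equation modelling as a secondary stage. It names no SES or psychopathology adjustment.

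**Shared risk.** The Introduction of the Combined protocol and SAP says that "low SES is a major risk factor for both intrauterine growth retardation (IUGR) and pre-term labour", that "ADD is far more prevalent in low SES environments", and that "the risk factors for IUGR, including maternal stress, maternal psychopathology, protein malnutrition, tobacco/alcohol consumption are identical to those for ADD". Under Hypothesis 2 the Protocol expects that mother-infant interaction "will be influenced by the quality of the maternal environment and maternal mental well being"; the Analyses section repeats that it "will be associated with differences in the quality of the maternal environment and maternal mental well-being".

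**The concern.** This is an observational cohort. On the documents' own account, SES and parental psychopathology can be related to the exposure (birth weight), the moderator (attachment) and the outcome (child symptoms). A model holding only birth weight class and attachment then credits part of the family's influence to birth weight.

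The exposed quantities are the birth weight class effect and the class contrast among insecure children, which the plan uses to interpret the interaction. The interaction test is exposed in two cases only: the family factor's effect differs by attachment, or it differs by birth weight class while the factor is also related to attachment. The second case is plausible because the Protocol (Background) says that more vulnerable children, including those of low birth weight, "appear to be at increased sensitivity to the quality of the post-natal environment".

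At stake is whether a positive birth weight result can be read as an effect of fetal growth.

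**Working it through.** The plan gives no power or error rate for this ANOVA, so there is no figure to reproduce. The size was explored by simulation within one gender stratum, with no true birth weight effect.

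**Inputs from the documents.** Birth weight classes 0-20, 21-40 and 41-70%; attachment secure or insecure; about 600 children enrolled. Half of 600 is 300 per stratum. That is an upper bound, since it assumes that all are assessed and none lies above the 70th percentile. N = 150 was also run.

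**Assumed inputs.** One shared cause C; 40% insecure; strength r = 0.20, 0.25 or 0.30; correlation of C with attachment liability (rho) 0, 0.2 or 0.4. No document supplies these values.

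**Model.** z is the normal quantile of the birth weight percentile, uniform on 0-70%. C = -r z + error, with variance 1 - r² given z. Score = slope x C + error. The slope is r in the additive case. There were 5,000 runs per setting, so the standard error is 0.3 to 0.5 points.

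**Spurious gap, additive case.** Mean z is -1.400 in the lowest class and +0.129 in the highest. The gap is r² x (0.129 + 1.400):
- r = 0.20: 0.0400 x 1.529 = 0.061 SD
- r = 0.25: 0.0625 x 1.529 = 0.096 SD
- r = 0.30: 0.0900 x 1.529 = 0.138 SD

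**False-positive rates at nominal 5%, unadjusted, additive, N = 300, rho = 0:**

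| r | class test | class test, insecure only | interaction |
|---|---|---|---|
| 0.20 | 5.5% | 5.1% | 4.9% |
| 0.25 | 7.7% | 5.9% | 5.2% |
| 0.30 | 12.9% | 7.6% | 4.7% |

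At N = 150, over all rho, the ranges are 5.4-9.1%, 4.8-6.6% and 4.4-5.4%.

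**Effect of C stronger in insecure children** (slope 1.5r against 0.5r, rho = 0.2, N = 300). Insecure-only contrast: 6.1, 7.5 and 11.7%. Interaction: 5.3, 6.0 and 7.4%.

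**Effect of C varying by birth weight class** (rho = 0.4, N = 300). Interaction: 5.5, 7.7 and 7.6% unadjusted; 5.8, 7.5 and 7.0% with C and C x attachment; 4.7, 5.0 and 4.9% once C x class is added.

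**After adjustment.** Adding C returns the class and insecure-only rates to 4.2-5.9% in the additive and attachment-varying settings.

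**Multiplicity.** Correction does not remove the bias. At 0.05/7 = 0.71%, for seven DOMINIC-R scales, the class test rate is 0.9-3.2% at N = 300.

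**Cross-check.** A separate model used a binary low SES factor at 35%, the projected share in the growth-restricted group (31/(31 + 57) = 31/88). It assumed odds ratios of 1.5-2.5 with birth weight class and with attachment, an outcome effect of 0.4 SD, and a further 0.4 SD in insecure children. At N = 300 the insecure-only rate was 7.0-11.8% unadjusted and 5.0-6.1% adjusted; the interaction was 5.3-5.5% unadjusted.

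**The case against.** **The hypothesis is the interaction, and it is robust.** This largely stands. The interaction rate is near 5% under additive confounding and about 7-7.7% at worst. The insecure-only contrast is a post-hoc step, so its unconditional rate overstates how often it would be reported. But the Protocol also predicts birth weight effects in their own right, and those carry the bias.

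**The sampling may undo the association.** The Combined protocol and SAP (III. Methods) plans to oversample low SES babies of normal weight. That could weaken or reverse the link between SES and birth weight in the sample. Whether it carried through to the roughly 600 children is not stated. This stands: neither size nor direction can be read from the documents. It is no reason to omit SES, since sampling then depends on SES.

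**Attachment already carries SES.** The Introduction says SES effects disappear once parental care is controlled. Attachment may absorb part of the SES effect, but a secure/insecure split is a coarse proxy for care and does not represent parental psychiatric history.

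**The section is deliberately partial.** It says it concentrates on new measures, and it leaves ANCOVAs open. A reader might infer that the plan rules out covariates; it does not. But the ANCOVAs are optional, concern moderators and name only sleep, while the Family History Screen is itself given no role in the analysis.

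**Full adjustment can remove the effect under test.** If quality of care drives the moderation and SES tracks care, an SES x birth weight class term absorbs part of the hypothesised effect. This stands. With moderation through latent care (correlated 0.8 with attachment liability, N = 300) and SES and parental history each entered with both products, simulated interaction power fell from 48 to 45%, 46 to 36% and 47 to 25% at covariate-care correlations of 0.2, 0.4 and 0.6. Covariate plus covariate x attachment cost about 1 point or less.

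**Conclusion.** The omission is real and worth correcting. Birth weight class effects, and the birth weight contrast among insecure children, could partly reflect shared family risk. With r assumed at 0.20-0.30 and N = 300 per stratum, the class test rate is about 6-13% under additive confounding. At the low end, or at smaller N, the inflation is slight.

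Two stronger readings are not supported. A reader might infer that the Hypothesis 1 interaction test is invalid; it stays near nominal unless the family factor's effect varies, and even then rises only modestly. A reader might also infer that birth weight effects will be overstated; the planned oversampling leaves the direction open.

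The shared-risk statements quoted come from the 2004 document. The 72-month Protocol supports them in part, naming maternal stress and depression among predictors of growth restriction.

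**What to change.** - **Primary model.** Keep birth weight class x attachment within gender strata. Prespecify SES, recorded at or nearest to pregnancy, and SES x attachment as added terms. Report the unadjusted ANOVA alongside.
- **Sensitivity models only.** (a) Parental psychiatric history from the Family History Screen, noting that it is a lifetime measure taken at 72 months and may include episodes after birth. (b) Prenatal depressive symptoms, stress, smoking and alcohol together, because the Protocol treats these as adversity that birth weight marks. (c) Covariate x birth weight class products, noting that they guard against class-varying confounding but can absorb the hypothesised birth weight x care effect.
- **Wording.** Describe birth weight effects as associations.

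**Cost.** A change of analysis wording. If SES is one continuous term, the primary model uses 1 + 1 = 2 further degrees of freedom per stratum. The 2004 plan already groups mothers by SES, and its 6-month household checklist has socio-economic items. Whether SES is held for all of the roughly 600 children is not stated, so some missing covariate data should be expected.
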